- g. Vital signs (blood pressure, temperature, pulse) measured in sitting position. On Cycle 1 Day 1: before the start of daratumumab infusion; at 0.5, 1, 1.5, 2, 3.5 hrs after the start of the infusion; at end of infusion; and 0.5, 1 hr after end of infusion. If an IRR occurred during the infusion due to which infusion is stopped and later the infusion is resumed, the site will follow initial infusion start time point for the vital sign collection. For all other infusions, vital signs will be measured immediately before infusion start and at end of daratumumab infusion.
- h. Refer to SIPP for recommendations on daratumumab infusion rate. Administer pre- and postinfusion medications as per Section 5.3.
- i. May be performed with oral contrast only if the subject is intolerant of IV contrast agents. If other areas of disease are involved, they can be imaged by either CT or MRI. All scans will be collected and reviewed centrally. The similar methodology should be used throughout the study.
- j. Refer to the laboratory manual for the detailed instructions for the whole blood collection.
- k. Follow-up will begin once a subject discontinues study treatment; if subject discontinues due to PD, follow-up will occur at least every 8 weeks (± 2 weeks). If subject discontinues due to other reasons (not PD), follow-up will occur at least every 8 weeks (± 2 weeks), including regular scheduled scan until PD is confirmed, and follow-up visit will be continued after PD confirmation.
- l. If more than one IRRs occurs during dose administration, blood sample should be collected only when the first IRR occurs.
- m. Tumor biopsy may be conducted as clinically indicated and is strongly recommended if lesion is reasonably accessible to confirm suspected PD.
- n. If PET/CT or CT or MRI is performed before ICF signed date due to site's routine practice and if it fulfills the study requirement in the image manual, those image data will be considered as baseline image data as long as the image scanned date is within 21 days prior to Cycle 1 Day 1.
- o. B-Symptoms assessment is also required to be collected in every disease evaluation assessment date.
- p. Local testing for HBsAg, Anti-HBs, and Anti-HBc. Refer to Section 8.6.
- q. For subjects with serologic evidence of resolved HBV infection (ie, positive Anti-HBs or positive Anti-HBc) at Screening, HBV DNA testing by PCR must be performed locally. Refer to Section 8.6.

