9.2. Discontinuation of Study Treatment/Withdrawal From the Study

Discontinuation of Study Treatment

If a subject's study treatment must be discontinued, it will not result in automatic withdrawal of the subject from the study. The EoT Visits and Follow-up visit assessments should continue as specified in the [T&E Schedule](#).

A subject's study treatment (daratumumab) should be discontinued if:

- The investigator believes that for safety reasons or tolerability reasons (eg, AE) it is in the best interest of the subject to discontinue study treatment
- The subject becomes pregnant
- The subject withdraws consent for administration of study drug
- The subject initiates treatment with a prohibited medication
- The subject received concurrent (non-protocol) treatment for NKTCL
- The subject experiences unacceptable toxicity, including IRRs described in [Section 5.3](#)

- The subject's dose of daratumumab is held for more than 4 weeks in Cycles 1-6 or for more than 6 weeks in Cycle 7 and beyond (unless sponsor approves continuation)
- The subject experiences PD (see below and [Attachment 6](#)). Relapse from CR is not considered as disease progression.
- Daratumumab becomes commercially available (or when daratumumab can be accessed from another source) for this disease. At this time, the subject will be transitioned from study drug to commercial product and will be withdrawn from the study. In these circumstances, the sponsor and investigator will support transition of the subject to ensure that treatment continues and remains uninterrupted.
- A subject who experiences a second primary malignancy that cannot be treated by surgery or radiotherapy alone must be withdrawn from the study. However, a subject who develops a malignancy that can be cured surgically or with definitive radiotherapy may continue to receive the assigned study treatment and should continue to be followed for subsequent progression of NKTCL.

Subjects should be discontinued from study treatment if they have objective radiological PD based on real time BICR according to LUGANO Classification. Following centrally confirmed radiological PD subjects will be discontinued from study treatment and enter the Follow-up phase.

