For subjects who have PD as evidenced by unambiguous clinical information (eg. pathologically demonstrated as PD), before such subjects discontinue study treatment due to PD, sites will document PD by completing and faxing a PD form to the sponsor as soon as possible and within 48 hours of PD assessment; EoT steps will be performed. The study responsible physician will confirm that treatment should be discontinued. After confirmation from the sponsor, study treatment may be discontinued and the subject can enter into Follow-up phase. If a subject discontinues study treatment for any reason other than PD, then disease assessments should be obtained as specified in the [T&E Schedule](#).

Withdrawal From the Study

A subject will be withdrawn from the study for any of the following reasons:

- Lost to follow-up
- Withdrawal of consent
- Death
- Sponsor terminates the study.

If a subject is considered lost to follow-up, every reasonable effort must be made by the study-site personnel to contact the subject and determine the reason for discontinuation/withdrawal. The measures taken to follow up must be documented.

When a subject withdraws before completing the study, the reason for withdrawal is to be documented in the eCRF and in the source document (refer Section [8.1.4](#) and Section [15.2.3](#) for details on collection of long-term survival status). Study drug assigned to the withdrawn subject

may not be assigned to another subject. Subjects who withdraw will not be replaced. If a subject withdraws from the study before the EoT, assessments should be obtained.

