10.3.2. Secondary Efficacy Endpoint

Complete response (CR) rate is defined as the proportion of subjects who achieve CR based on BICR and will be analyzed similarly as the primary efficacy endpoint.

Progression-free survival (PFS) is defined as the duration from the date of the first daratumumab dose to the date of progression/relapse based on BICR or death, whichever comes first. For those subjects who are still alive without progression/relapse, PFS will be censored at the last adequate tumor assessment.

Duration of response (DoR) will be duration from the date of the initial documentation of a response to the date of first documented evidence of PD based on BICR (PD; or relapse for subjects who experience CR) or death. For those subjects who are still without progression/relapse, DoR will be censored at the last adequate tumor assessment.

Time to response is defined as the duration from the date of the first dose of daratumumab to the earliest date that a response (CR/PR based on BICR) is first documented. For nonresponders, it will be censored at the date of PD/relapse or the date of the last adequate disease assessment, whichever comes first.

Overall survival (OS) is defined as the duration from the date of the first daratumumab dose to the date of death. For those subjects who are still alive without progression/relapse, OS will be censored at the last date known to be alive.

For time to event endpoints (eg, PFS, OS, time to response, DoR), Kaplan-Meier estimates will be presented. Median along with corresponding 95% CIs will be obtained from the Kaplan-Meier estimates. Analysis for time to response and DoR will be for responders only.

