5.2.1. Definition

Objective response rate (ORR) is defined as the proportion of subjects who achieve CR or PR per Revised Criteria for Response Assessment of Hodgkin and non-Hodgkin lymphoma: LUGANO classification based on BICR.

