5.3.1. Definition

Complete response (CR) rate is defined as the proportion of subjects who achieve CR based on BICR and will be analyzed similarly as the primary endpoint ORR.

Progression-free survival (PFS) is defined as the duration from the date of the first daratumumab dose to the date of progression/relapse based on BICR or death, whichever comes first. For those subjects who are still alive without progression/relapse, PFS will be censored at the last adequate tumor assessment. Subjects who are progression-free and alive or have unknown status will be censored at last tumor assessment. Subjects with no post baseline disease assessment will be censored on Day 1. Subjects who started a subsequent anti-cancer therapy in the absence of progression will be censored at the last disease assessment before the start of subsequent therapy. Subjects whose diseases have not progressed and who are still alive at the end of the study or clinical cutoff will be censored at the last adequate disease assessment.

Duration of response (DoR) will be duration from the date of the initial documentation of a response to the date of first documented evidence of progressive disease based on BICR (PD; or relapse for subjects who experience CR) or death and calculated only for responders. For those subjects who are still without progression/relapse, DoR will be censored at the last adequate tumor assessment.

Time to response (TTR) is defined as the duration from the date of the first dose of daratumumab to the earliest date that a response (CR/PR based on BICR) is first documented. Descriptive analysis will be performed for responders including median, mean, standard deviation, and range.

Overall survival (OS) is defined as the duration from the date of the first daratumumab dose to the date of death. Subjects who withdraw consent from the study or are lost to follow-up will be censored at the time of withdrawal or lost to follow-up. For those subjects who are still alive at the time of analysis, OS will be censored at the last date known to be alive.

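### SAP 5.3.1 censors PFS at subsequent anticancer therapy but not duration of response, so a responder's DoR can exceed the same subject's PFS

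*SAP*

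**What the plan says.** **Protocol 10.3.2** treats the two endpoints in the same way. Each ends at BICR progression or relapse, or at death. Otherwise it is censored at the last adequate assessment; for PFS: "For those subjects who are still alive without progression/relapse, PFS will be censored at the last adequate tumor assessment". Neither has a rule for subsequent therapy.

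**SAP 5.3.1** adds one to PFS: "Subjects who started a subsequent anti-cancer therapy in the absence of progression will be censored at the last disease assessment before the start" of that therapy. The DoR paragraph in the same section keeps the protocol's form. BICR progression, relapse or death is an event at any time; failing that, "For those subjects who are still without progression/relapse, DoR will be censored at the last adequate tumor assessment". No other SAP section closes the gap: 5.1.2 deals only with imputation and 5.3.2 only with presentation.

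**Follow-up after new therapy.** Protocol 9.2 lists "The subject received concurrent (non-protocol) treatment for NKTCL" among the reasons to stop study drug, and then says "The EoT Visits and Follow-up visit assessments should continue as specified in the" Time and Events Schedule. Protocol 8.1.4 stops scheduled scans at the start of new anticancer therapy, but subsequent therapy and survival status are still recorded.

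**Response rate.** SAP 5.2.1 reads "Objective response rate (ORR) is defined as the proportion of subjects who achieve CR or PR per Revised Criteria for Response Assessment", by BICR. It sets no time limit relative to subsequent therapy.

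**The concern.** DoR begins at first response, PFS begins at first dose, and the two share their end events. Under one set of rules, DoR cannot be longer than PFS in the same subject. Once PFS is cut at new therapy and DoR is not, that ordering can fail. A death on other therapy is then charged to the daratumumab response, and the time spent on that therapy is counted in it, while PFS does neither.

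The trigger is plausible. Protocol 8.1.3 lets a subject stop treatment on unambiguous clinical progression without BICR confirmation. A responder who does so and moves to other therapy has no BICR progression date. What is at stake is the coherence of two estimates that readers will set side by side to judge whether responses last.

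**Working it through.** The plan states no figure for DoR, so the check is a constructed case run through the written rules.

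**Inputs**
- Day count, SAP 2.1: end date minus start date, plus 1 day.
- Scan times, Protocol 8.2: every 8 weeks for the first 6 months, so weeks 8 and 16 are scheduled scans.
- Constructed history: first response at week 8, still in response at week 16, new therapy at week 18 without BICR progression, no scans after that (as 8.1.4 requires), death at week 30.
- With first dose on Day 1, week *w* falls on Day 7*w* + 1. Week 8 is Day 57, week 16 is Day 113 and week 30 is Day 211.

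**Results**

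| Rule set | PFS | DoR |
|---|---|---|
| Protocol 10.3.2 | 211 − 1 + 1 = 211, event | 211 − 57 + 1 = 155, event |
| SAP 5.3.1 as written | 113 − 1 + 1 = 113, censored | 211 − 57 + 1 = 155, event |
| SAP with the PFS rule applied to DoR | 113, censored | 113 − 57 + 1 = 57, censored |

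When both endpoints stop on the same date, PFS minus DoR equals the response date minus the first-dose date. Here that is 57 − 1 = 56 days, and it can never be negative. Rows one and three satisfy this (211 − 155 = 56; 113 − 57 = 56). The SAP as written gives 113 − 155 = −42 days, and the same subject is censored on one endpoint and an event on the other.

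**Would the death be observed?** Protocol 3.1 places study end about 9 months after the last subject's first dose. Nine months is about 9 × 52/12 = 39 weeks, so a week-30 death falls within follow-up for every subject. At the primary analysis (about 6 months, or 26 weeks) it would be seen only in subjects dosed at least 4 weeks before the last one.

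**The primary decision rule.** The stated design does reproduce. For at least 8 responses in 32, exact power at 30% is 0.781 with binding futility and 0.788 without, against the stated 78%. Exact one-sided alpha at 15% is 0.094 and 0.096 respectively, under the stated 10%. The DoR mismatch does not touch these figures.

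**The case against.** **Small practical weight.** SAP 5.3.2 makes DoR descriptive and 5.1.1 sets no significance level. Only responders contribute, and 8 are enough for success. A responder who starts other therapy with no BICR progression is an unusual case, and the documents give no frequency. In the worked case the extra DoR outcome is a death, so the rule does not systematically flatter daratumumab. All of this stands and limits the severity.

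**The word adequate.** One could argue that the last adequate assessment already excludes scans after new therapy. The SAP does not define the term. PFS uses it and still needed a separate sentence on subsequent therapy. In any case it governs censoring only, and a death remains a DoR event.

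**A stronger reading for the response rate.** Because SAP 5.2.1 has no cut, a reader might infer that responses to other therapy would count toward 8 of 32 and inflate alpha. The documents do not support that as an expected result. Protocol 8.1.4, the section on post-treatment follow-up, ends scheduled scans at new anticancer therapy. Protocol 9.2 says "If a subject discontinues study treatment for any reason other than PD, then disease assessments should be obtained as specified in the" schedule, and footnote k there speaks of "including regular scheduled scan until PD is confirmed"; neither that footnote nor 8.2 names new therapy as a stop. Both are abbreviated lists, however, and neither names death as a stop either. What remains is a narrow path: a site following the looser wording, or an unscheduled scan, since 8.2.6 sends all scans to BICR. No number of such subjects is given. The 79% response rate that the protocol introduction cites for the SMILE regimen is not a fair rate for subjects who, under inclusion criterion 3.1, are not candidates for other treatment.

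**A stronger reading for DoR.** A reader might also infer that clean scans on other therapy will lengthen DoR. That again requires scanning beyond the 8.1.4 stop. The death route does not.

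**Conclusion.** The concern holds for DoR. Following SAP 5.3.1 as written gives an internally inconsistent result: in the worked case, PFS censored at 113 days beside a DoR event at 155 days. This rests on three things: a responder starting other therapy before BICR progression, a later death captured in survival follow-up, and reading progression in the PFS sentence as BICR progression, which is how that section defines PFS. The timings are illustrative and no rate is claimed.

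The direction of any effect on the Kaplan-Meier DoR median is not fixed, because a late event replaces an early censoring. The consequence is limited to a descriptive secondary endpoint in a small number of responders.

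For the response rate, the missing cut is a gap in the definition. If 8.1.4 is followed, its effect on the 8-of-32 rule should be near zero. This is a minor point, worth correcting because the correction is so simple.

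**What to change.** **SAP 5.3.1, DoR paragraph.** Add: *Responders who begin subsequent anticancer therapy without prior BICR-assessed progression are censored at their last adequate disease assessment preceding that therapy.*

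**SAP 5.2.1, as a safeguard only.** Add: *A CR or PR counts when BICR documents it before BICR-assessed PD and before any subsequent anticancer therapy; the denominator remains all treated subjects.* The reference to BICR matters. Protocol 8.1.3 allows treatment to continue after progression seen only locally, and a cut at local progression could discard valid responses.

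**Cost.** Two SAP sentences, with no added subjects, visits or data. The start of subsequent therapy is already collected and already used for PFS. SAP 2.7.5 imputes only a missing day, so a start date lacking month or year would need a query, as it does for PFS now. Responses documented before other therapy still count. Changing the scan-stop wording in Protocol 8.2 or footnote k is not needed once the SAP has the cut, and would require a formal amendment under Protocol 16.1.

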5.3.2. Analysis Methods

Descriptive analysis will be performed for secondary endpoints. The Kaplan-Meier method will be used to estimate the distribution of PFS, OS and DoR. The number of events, subjects censored, the estimate of medians, and 95% confidence interval for medians will be presented. Plots of PFS, OS and DoR using Kaplan-Meier method will be presented. For CR rate, point estimate as well as

exact 95% CI will be provided. For TTR, mean, standard deviation, and range will be provided for responders.

6. SAFETY

Unless specifically stated, the observations that occurred during treatment period (i.e., within 30 days from the last study drug dosing) will be used for safety analyses. All observations will be presented in listings.

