Note: The start of each cycle may occur ± 3 days of the scheduled day in order to accommodate the schedule of the site or subject. For Cycles 1-6, there may be ± 1 day window for the scheduled infusion within the cycle. The EoT visit may occur $+7$ days of scheduled day. After PD is documented, subjects will continue to be followed for survival, second primary malignancies, and subsequent anticancer therapy.

TIME AND EVENTS SCHEDULE: PK AND IMMUNOGENICITY (ALL SAMPLES SHOULD BE SENT TO THE CENTRAL LABORATORY)

	Treatment Phase																	EoT ^d	Follow-up Phase	
	Weekly for 8 infusions				Biweekly for 8 infusions				Once every 4 weeks											
Cycle	Cycle 1				Cycle 2				Cycle 3	Cycle 4	Cycle 5	Cycle 6	Cycle 7	Cycle 9	Cycle 11	Cycle 12	Cycles 13, 15, 17+			
Study Day (Day)	1	8	15	22	1	8	15	22	1	1	1	1	1	1	1	1	1		FU-Wk4 ^d	FU-Wk8 ^d
Visit Window (day)	0	±1	±1	±1	±3	±1	±1	±1	±3	±3	±3	±3	±3	±3	±3	±3	±3	+7	±7	±14
Study Drug Administration ^a	X	X	X	X	X	X	X	X	X	X	X	X	X	X	X	X	X			
Pharmacokinetic Samples																				
Before Infusion (within 2 hours before the start of infusion)	X	X		X	X			X	X	X	X	X	X	X	X	X	X ^b	X	X ^c	X
End of infusion (within 2 hours after end of infusion)	X							X	X											
Immunogenicity Samples (NO additional immunogenicity samples needed and will be taken from PK samples for the planned time points.)																				
Before Infusion (within 2 hours before the start of infusion)	X												X			X		X	X ^c	X

Footnote:

- For complete study drug administration schedule beyond Cycle 3, refer to the main Time and Events Schedule.
- Samples will be collected at every other dose from Cycle 13+, ie, at Cycle 13, 15, 17, etc.
- If EoT sample is collected within 3-5 weeks after the last dose, ie, the window of FU-Wk4 visit, then FU-Wk4 sample does not need to be collected.
- The EoT is within 30 days (+7) of the last dose. FU-Wk4 and FU-Wk8 is 4 weeks (±7 days) and 8 weeks (±14 days) from the last dose, respectively.

ABBREVIATIONS

ADCC	antibody-dependent cell-mediated cytotoxicity
ADCP	antibody dependent cellular phagocytosis
AE	adverse event(s)
ANC	absolute neutrophil count
Anti-HBc	antibodies to hepatitis B core antigen
Anti-HBs	antibodies to hepatitis B surface antigen
BICR	blinded independent central review
CDC	complement dependent cytotoxicity
CI	confidence interval
CIP	Complement Inhibitory Protein
CNS	central nervous system
COPD	chronic obstructive pulmonary disease
CR	complete remission
CT	computed tomography

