3. STUDY DESIGN AND RATIONALE

3.1. Overview of Study Design

This is an open label, single arm, multicenter, Phase 2 study to evaluate the efficacy and safety of daratumumab monotherapy in subjects with relapsed and refractory extranodal NKTCL, nasal type. The study is a Simon's 2-stage design with up to 32 subjects to be enrolled. Following that, additional patients (ie, approximately 35 patients) may be enrolled in an expansion phase.

Subject participation will include a Screening Phase, a Treatment Phase, and a Follow-up Phase. The Screening Phase will be up to 21 days prior to Cycle 1, Day 1. Prior to enrollment, diagnosis of NKTCL must be verified by the sponsor from the local pathology report. Before enrollment to the study, sites will be required to provide archival or fresh tumor samples for assessment of CD38 expression. Fresh biopsy samples are preferred if available. Otherwise, archived formalin-fixed, paraffin-embedded (FFPE) blocks/slides are also acceptable.

The Treatment Phase will extend from Cycle 1, Day 1 until study drug discontinuation. After the first dose, disease evaluations will occur every 8 weeks for the first 6 months and thereafter, every 16 weeks. Subjects will be monitored for safety and assessed for PK and immunogenicity according to the scheduled assessments in the Time and Events (T&E) schedules ([T&E Schedule](#) and [T&E Schedule: PK and Immunogenicity](#)). Subjects will be treated until PD, unacceptable toxicity, or other reasons as listed in the protocol. End-of-Treatment (EoT) Visit is to occur within 30 days (+7-day window) after the last dose of all study treatments.

The Follow-up Phase will begin once a subject discontinues study treatment, and will continue until death, lost to follow up, consent withdrawal for study participation, or end of study, whichever occurs first. The follow-up schedule is presented in the [T&E Schedule](#).

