6.3. Clinical Laboratory Tests

Laboratory data will be summarized by type of laboratory test. Descriptive statistics will be calculated for each laboratory analyte at baseline and for observed values and changes from baseline at each scheduled time point. Changes from baseline results will be presented in pre-

versus post-treatment cross-tabulations (with classes for below, within, and above normal ranges). Frequency tabulations of the abnormalities will be made. A listing of subjects with any laboratory results outside the reference ranges will be provided. A listing of subjects with any markedly abnormal laboratory results will also be provided.

NCI-CTCAE version 4.03 will be used to derive toxicity grades for clinical laboratory tests when applicable. Shift tables from baseline to worst value on study (from treatment start to 30 days after last dose or the End of Treatment visit date, whichever is later) will also be provided. The worst toxicity grade during the study will be tabulated.

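### The End-of-Treatment visit may fall up to 37 days after the last dose, but SAP 6 closes the ECG and by-visit laboratory summaries at 30 days; only the laboratory shift-table paragraph extends the window

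*SAP*

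**What the plan says.** SAP 6 sets the default window for the whole safety chapter: "the observations that occurred during treatment period (i.e., within 30 days from the last study drug dosing) will be used for safety analyses". The default applies unless an exception is specifically written. The next sentence adds: "All observations will be presented in listings".

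The protocol's visit window is wider. Protocol 3.1 states: "End-of-Treatment (EoT) Visit is to occur within 30 days (+7-day window) after the last dose of all study treatments". Protocol 8.1.3 and the PK and immunogenicity schedule repeat the same 30 + 7 days. The main Time and Events Schedule places haematology, clinical chemistry and a 12-lead ECG at EoT. ECGs are otherwise scheduled only at screening, Cycle 3 Day 1 (C3D1) and Cycle 6 Day 1 (C6D1).

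The safety chapter of the SAP writes one exception to the default. In SAP 6.3, the shift tables from baseline to worst value run "from treatment start to 30 days after last dose or the End of Treatment visit date, whichever is later". The same paragraph continues: "The worst toxicity grade during the study will be tabulated". The preceding paragraph of 6.3 covers the by-visit statistics ("Descriptive statistics will be calculated for each laboratory analyte at baseline and for observed values and changes from baseline at each scheduled time point"), the normal-range cross-tabulations and the abnormality frequencies, and gives no window. SAP 6.4, on ECG, gives none either.

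**The concern.** A visit 31 to 37 days after the last dose complies with the protocol but lies outside the default analysis window. The SAP's authors dealt with this for one set of laboratory tables and left the rest of the same visit's data under the default. Two outputs from one visit are therefore treated differently, and two programmers could reasonably produce different ECG tables.

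ECG is the more exposed of the two. Haematology and chemistry are measured repeatedly from Cycle 1, so losing the EoT record costs a subject one time point. Post-baseline ECGs are sparse. For a subject who stops during Cycles 1 or 2, the EoT ECG is the only scheduled one after baseline, and omitting it can remove that subject from the ECG change-from-baseline and abnormality tables. Early discontinuations, including those for toxicity, are subjects whose safety data a reader would want to see.

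**Working it through.** The plan gives no figure to reproduce here. The check is calendar arithmetic plus a comparison of the SAP 6 subsections.

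**Step 1: the gap.** Inputs are the 30-day default (SAP 6) and the EoT window of 30 days plus 7 (Protocol 3.1).
- Latest in-window EoT visit: 30 + 7 = day 37 after the last dose.
- Default cut-off: day 30 after the last dose.
- Gap: days 31 to 37, which is 37 − 30 = 7 days. A visit on or before day 30 is unaffected.

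**Step 2: where the gap applies.** Take an EoT visit on day 34 as an example.

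| Output | Window stated | Day-34 record |
|---|---|---|
| Laboratory shift tables (SAP 6.3) | later of 30 days and EoT date | summarised |
| Laboratory worst grade (SAP 6.3) | same paragraph, study-wide wording | arguably summarised |
| Laboratory by-visit statistics, cross-tabulations, abnormality frequencies (SAP 6.3) | none, so default | left out |
| ECG statistics and abnormalities (SAP 6.4) | none, so default | left out |
| Listings (SAP 6) | all observations | shown |

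Vital signs are not scheduled at EoT, so SAP 6.5 is not affected.

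**Step 3: who depends on the EoT ECG.** With 28-day cycles, C3D1 is study day 1 + 2 × 28 = 57. The last planned dose before it, Cycle 2 Day 22, is study day 28 + 22 = 50. A subject who stops before C3D1 has a screening ECG and an EoT ECG scheduled, with none in between.

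**Step 4: size.** The documents state neither how many subjects stop before C3D1 nor when EoT visits take place, so the number cannot be derived. Under stated assumptions,

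affected subjects = 32 × (proportion stopping before C3D1) × (proportion of their EoT visits on days 31 to 37).

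- 10% and 10%: 32 × 0.10 × 0.10 = 0.32
- 30% and 30%: 32 × 0.30 × 0.30 = 2.88
- 50% and 50%: 32 × 0.50 × 0.50 = 8.0

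Both proportions are assumptions. The range runs from a fraction of one subject to a quarter of the 32.

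**Step 5: after the change.** With the 6.3 window applied to these outputs, an EoT visit on any of days 31 to 37 falls inside the analysis window and the gap closes.

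**The case against.** The strongest defence is that the SAP already covers these records. SAP 6.3 and 6.4 summarise by scheduled time point, and EoT is a scheduled time point for haematology, chemistry and ECG. SAP 2.1 uses the nominal cycle for data collected by cycle, and it ends the last cycle at the EoT visit date. Protocol 10.8 plans the ECG statistics without a 30-day limit. A programmer could keep the nominal EoT record on that basis. This shows that the omission was probably not intended, but it does not settle the matter: SAP 6 requires an exception to be specifically stated, and 6.3 shows the form the authors use when they mean one.

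Other parts of the defence stand, and they rule out stronger conclusions that a reader might draw:

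- *That EoT data are discarded.* They are not. Every observation appears in the listings; what is lost is inclusion in the summaries.
- *That all safety analyses stop at day 30.* The laboratory shift tables expressly do not, and the worst-grade table probably does not.
- *That EoT visits in general are affected.* Only those on days 31 to 37 are. Cycles 1 and 2 are dosed weekly, and Protocol 8.1.3 asks sites to try to hold the visit before subsequent treatment starts. Both may bring EoT forward in the early stoppers who matter most here.
- *That late discontinuers also vanish from the ECG tables.* From Cycle 7 the four-weekly dosing makes an EoT visit near or after day 30 plausible, but those subjects already have ECGs scheduled at C3D1 and C6D1. They could lose a time point, but not their place in the tables.
- *That early stoppers have no other post-baseline ECG.* The EoT ECG is the only scheduled one; unscheduled ECGs may exist.
- *That a definite share of subjects is lost.* Nothing in the documents supports a single percentage.

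**Conclusion.** The mismatch is real but narrow. As written, an in-window EoT ECG or by-visit laboratory value obtained 31 to 37 days after the last dose is listed but left out of the summaries. A subject who stops before C3D1 could therefore be absent from the ECG change-from-baseline and abnormality tables despite a compliant visit. This rests on reading the SAP 6 default literally, with 6.3 as the only exception stated in that chapter. The illustrative range of 0.3 to 8 of 32 depends wholly on the two assumed proportions and should not be quoted as an estimate.

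Severity is low. The safety analysis is single-arm and descriptive. The AE tables, the efficacy endpoints and the futility rule do not depend on these records.

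**What to change.** Add one sentence to SAP 6: for ECG and for visit-based laboratory summaries (descriptive statistics, normal-range cross-tabulations and abnormality frequencies), the analysis window ends at the later of 30 days after the last dose and the EoT visit date. This is the window SAP 6.3 already uses for the shift tables. The same sentence can confirm that it governs the worst-grade table.

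Keep 30 days for AE onset, in line with SAP 6.1 and the AE collection period in Protocol 11.3.1.

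The cost is one SAP sentence and the matching programming specification. It needs no new data, visits or protocol amendment.
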